### 14.3. Sample Size Justification

Since this study is a workflow study with no primary hypotheses to be tested, there are no statistical power calculations. Evidence from between 30 to 50 prospectively enrolled subjects are deemed sufficient to characterize safety and performance of the Qdot-nGen ablation system.

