	The QDOT-nGEN study is a prospective, multi-center, non-randomized, interventional clinical workflow study.						

Sample Size and Statistical Analysis	Up to 50 subjects with a minimum of 30 subjects undergoing a study ablation						
Statistical Analysis	procedure will be enrolled.						
	This study is a workflow study, there is no statistical power calculation and no						
	hypothesis will be tested. Descriptive statistics will be presented. Thirty subjects (30) undergoing an ablation procedure are deemed enough to characterize safety and						
	acute performance.						
Study Population	Subjects with AF who are scheduled to undergo a clinically indicated ablation						
	procedure for management of their AF will be the target population for screening						
Geographic areas to be included	e Up to 6 centers in Canada						
Study Duration	Approximately 9 months						
Participant Duration	Subjects will be followed until completion of the 3-month visit post-procedure						
Procedure Description	Subjects will arrive to the electrophysiology laboratory for their ablation procedure and will undergo preparation for the procedure per the hospital's standard protocol (discretion of investigator).						
	The AF Ablation procedure will follow below sequence:						
	
 
Esophageal monitoring to avoid injury is recommended when ablating near the esophagus
 
						
	Anatomical mapping of the left atrium						
	Introduction of the study catheter						
	
 
Circumferential Pulmonary Vein Isolation (PVI) primarily using QMODE+ mode
 
						
	
 
Confirmation of PVI with Lasso® or PentaRay® (or other at investigators discretion)
 
						
	Confirmation of entrance block with adenosine/isoproterenol challenge						
	In this study protocol, QMODE+ is to be used as the primary mode for pulmonary v isolation. Only after the investigator deems QMODE+ is unable to achieve PVI sho the study catheter in QMODE be used to complete the procedure.						
	Additional RF ablation lesion outside the PVs can be made by either QMODE+ or QMODE at the discretion of the physician.						
Primary Endpoints	Acute Performance:						
	Acute Procedural Success defined as confirmation of entrance block in all targeted PVs after adenosine and/or isoproterenol challenge using the nGEN / QDOT Micro Ablation System						
Additional Data	Adverse events:						

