# 2. Objectives

The objective of this study is to evaluate the workflow and acute performance of the QDOT MICRO™ catheter used in combination with the nGEN Generator with QDOT software module for the treatment of Patients with Atrial Fibrillation during standard electrophysiology mapping and RF ablation procedures. In this study, QMODE+ will be used as the primary mode for pulmonary vein isolation. If the investigator deems QMODE+ is unable to achieve PVI, the study catheter in QMODE will be used to complete the procedure.

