## 14.1. Levels of Significance

All data will be summarized by descriptive analyses. No formal statistical inference will be made.

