### 14.4. Analyses to be conducted

### 14.4.1. General Conventions

Standard descriptive summaries for continuous data include the number of observations with data, mean, standard deviation (SD), median, minimum, and maximum values. The mean and median will be rounded to one decimal place greater than in the raw data where applicable; the standard deviation will be rounded to two decimal places greater than in the raw data where applicable. In cases where this is not applicable (e.g., average time spent), the mean will be rounded to one decimal place; the standard deviation to two decimal places; the minimum and maximum to the nearest whole number. These will be referred to as "continuous summaries" in this document.

For categorical data, the count and percent will be provided. Percentages will be based on the number of subjects without missing data. For adverse event and device effects data, percentages will be based on the number of subjects in the analysis population being used in the analysis. When count data are presented, the percentage for zero counts will be suppressed in order to draw attention to the non-zero counts. Frequency counts will be presented as whole numbers and

percentages will be rounded to one decimal place. This will be referred to as "categorical summaries" in this document.

Adverse events (AE) tables will be sorted by decreasing frequency of events, unless otherwise specified.

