#### 14.4.4. Analysis for Primary Endpoint

Acute procedural success will be summarized using categorical summaries for the effectiveness analysis set.

A listing of the primary endpoint will be provided.

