### 14.4.6. Analyses of Secondary Safety Endpoints

Secondary safety endpoints will be analyzed using the safety analysis population.

An adverse event (AE) is an event recorded on the Adverse Event CRF page with an onset on or after the study ablation procedure. AEs with onset prior to this date that worsen in severity (i.e., increases in severity) after a subject has signed informed consent OR have a missing onset date are also considered an AE. AEs will be summarized both by subject and event. If a subject has multiple occurrences of an AE, for the by-subject summary only a single occurrence will be counted and for the by-event summary each event will be counted.

The overall incidence of AEs will be summarized by:

- Any adverse event;
- Serious adverse event;
- Non-serious adverse event;
- Device-related adverse event (defined as unlikely, possible, probable or having a causal relationship with the device);
- Serious device-related adverse event;
- Unanticipated device-related adverse event;
- Serious unanticipated device-related adverse event;
- Procedure-related adverse event (defined as unlikely, possible, probable or having a causal relationship with the procedure);
- Adverse events leading to discontinuation.

Serious AEs (SAE) and Non-Serious AEs (NSAE) will be summarized separately by overall incidence and adverse event term using categorical summaries.

An adverse device effect (ADE) is any event recorded to have led to an AE on the Investigational device deficiency CRF.

ADEs will be summarized by overall incidence, ADEs leading to an AE, ADEs leading to an SADE and unanticipated SADE (USADE), device, and time point during the procedure using categorical summaries.

Serious Adverse ADEs (SADE) will be summarized by overall incidence, SADEs leading to an AE, SADEs leading to a USADE, device, and time point during the procedure using categorical summaries.

ADEs, SADEs, and USADEs will be summarized by overall incidence and by adverse event term using categorical summaries in separate tables.

Listings of adverse events and device effects will be generated as well as device deficiencies.

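### Minor: the plan deems 30 to 50 subjects enough to characterize safety and performance without stating the precision, and reports its categorical endpoints as count and percent without intervals

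*Combined protocol and SAP*

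**What the plan says.** Two places justify the size. Section 14.3 says there is no hypothesis and no power calculation, then states: "Evidence from between 30 to 50 prospectively enrolled subjects are deemed sufficient to characterize safety and performance of the Qdot-nGen ablation system". The Protocol Summary says: "Thirty subjects (30) undergoing an ablation procedure are deemed enough to characterize safety and" acute performance. Neither adds an expected rate, a target width or any other measure of precision.

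The analysis is descriptive by design. Section 14.1 says: "No formal statistical inference will be made". For the primary endpoint, section 14.4.4 says: "Acute procedural success will be summarized using categorical summaries for the effectiveness analysis set". For safety, section 14.4.6 says: "Serious AEs (SAE) and Non-Serious AEs (NSAE) will be summarized separately by overall incidence and adverse event term using categorical summaries". Section 14.4.1 defines a categorical summary as count and percent, and adds that "the percentage for zero counts will be suppressed in order to draw attention to the non-zero counts". No confidence interval is planned anywhere in section 14.

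The two places count different subjects. Section 14.3 counts enrolled subjects, and section 4.5 defines these as patients who have signed consent. The Protocol Summary counts subjects who undergo ablation.

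**The concern.** To say that a sample characterizes safety and performance invites the question of how closely. The plan answers it neither in the justification nor in the planned tables. The likeliest results in a study of this size are those that a bare count and percent conveys worst: no or one serious event, and all or nearly all procedures successful. A zero row would show neither a rate nor a bound, and a 100% success rate would stand without its lower limit.

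What is at stake is how the results are read. Section 1.2.1 names acute safety as a main objective alongside acute device performance. A clean safety table from 30 subjects, next to a statement that the size is enough, could be taken to say more about uncommon events than it does. No margin, decision rule or stopping boundary depends on it.

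**Working it through.** **Is there a figure to reproduce?** No. The documents give no significance level, power, expected rate, margin or target width, so no formula leads to 30 or 50. The check is therefore what precision those sizes deliver.

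**Inputs.** n = 30 and n = 50 (section 14.3 and Protocol Summary), taken as subjects analysed. The two-sided 95% level and the observed counts are assumptions. Subjects are treated as independent with a common rate.

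**Exact (Clopper-Pearson) intervals.** For x events in n, the lower limit is the 0.025 quantile of Beta(x, n−x+1) and the upper limit is the 0.975 quantile of Beta(x+1, n−x). At the extremes these have a closed form:

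- Zero events, upper limit 1 − 0.025^(1/n): 1 − 0.025^(1/30) = 11.6%; 1 − 0.025^(1/50) = 7.1%.
- All successes, lower limit 0.025^(1/n): 88.4% at 30; 92.9% at 50.

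| Observed | n = 30 | n = 50 |
|---|---|---|
| No event | 0–11.6% | 0–7.1% |
| One event | 3.3% (0.1–17.2%) | 2.0% (0.1–10.6%) |
| Two events | 6.7% (0.8–22.1%) | 4.0% (0.5–13.7%) |
| All succeed | 100% (88.4–100%) | 100% (92.9–100%) |
| One failure | 96.7% (82.8–99.9%) | 98.0% (89.4–99.9%) |

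With zero events, the one-sided 95% upper bound, 1 − 0.05^(1/n), is 9.5% at 30 and 5.8% at 50.

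**Chance of seeing at least one event**, 1 − (1 − p)^n. Section 1.3.1 cites major complications at 0.8%, and below 5% at major centers. These rates serve only as a yardstick, since a major complication is not the same as a serious adverse event as defined in section 9.1.2.

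- p = 0.8%: 1 − 0.992^30 = 21%; 1 − 0.992^50 = 33%.
- p = 5%: 1 − 0.95^30 = 79%; 1 − 0.95^50 = 92%.
- Solving for an 80% chance, p = 1 − 0.2^(1/n): 5.2% at 30 and 3.2% at 50.

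So a table with no events at n = 30 remains compatible with rates up to 11.6%, above the under-5% range cited in the background.

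**Denominator.** Because enrolled means consented, 30 enrolled can mean fewer than 30 analysed. As an illustration, if 27 of 30 consented subjects had the device inserted, the zero-event upper limit would be 1 − 0.025^(1/27) = 12.8%.

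**The case against.** The strongest answer is that nothing here is wrong. The plan discloses that it has no hypothesis and no power calculation, and its analyses match. Section 2 states: "The objective of this study is to evaluate the workflow and acute performance of the" catheter with the generator. The Protocol Summary presents the study as additional confirmatory data, and section 1.2.1 describes two earlier catheter studies with 51 and 54 subjects. The plan nowhere claims to estimate the rates of uncommon events. All of this stands, and it keeps the point minor. It does not remove it: the plan chose to assert sufficiency for safety in two places, and a descriptive interval tests nothing and so leaves section 14.1 intact.

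Three stronger readings are tempting, and the documents do not support them.

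- A reader might infer that the sample is too small or that a power calculation is missing. With no hypothesis, there is nothing to power, and no stated figure is shown to be wrong.
- A reader might infer that zero-count suppression hides results. Only the percentage is dropped. The zero is still shown, the adverse event denominator is the analysis population, and section 14.4.2 reports the size of the sets, so a reader could derive the bound. The plan simply does not report it.
- A reader might infer that section 14 offers nothing but count and percent. That is true only of categorical endpoints. Continuous procedural data get mean, standard deviation, median, minimum and maximum, and listings are planned.

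Three limits on the remedy also stand. Section 8.2.2.3 has ablation continue until isolation is achieved, so an interval for acute success is less informative than one for events. Exact binomial intervals assume independent subjects with a common rate, while subjects come from up to 6 centers whose results may cluster. And two safety rows are not ready for an interval. Sections 9.1.3 and 14.4.6 word the adverse device effect differently. The procedure-related numerator includes events rated unlikely: "Procedure-related adverse event (defined as unlikely, possible, probable or having a causal relationship with the procedure".

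**Conclusion.** The point holds as a minor, cheap improvement and not as an error. The plan asserts that its size is sufficient without stating the precision, and reports its categorical endpoints without intervals. The precision is modest: an upper limit of 11.6% (n = 30) or 7.1% (n = 50) with no event, and a lower limit of 88.4% or 92.9% with no failure. These figures rest on the assumed two-sided 95% level, on independent subjects, and on 30 or 50 being the number analysed. Reporting intervals would not make the size adequate for rare events; it would show plainly that it is not.

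**What to change.** 1. In sections 14.4.4 and 14.4.6, add two-sided 95% Clopper-Pearson intervals for acute procedural success (effectiveness analysis set) and for the by-subject serious adverse event rate (safety analysis set). Label them descriptive, so that section 14.1 stands, and note that they assume independent subjects across centers. Use the denominator of the percentage that each interval accompanies. Add rows for serious adverse device effects and procedure-related events only after their definitions are reconciled.
2. In section 14.4.1, exempt these rows from the zero-count rule, so that a zero appears with its upper bound.
3. In section 14.3 and the Protocol Summary, replace the sufficiency wording with the precision by analysis set, for example: *If 30 (50) subjects are in the safety analysis set and none has a serious adverse event, the exact two-sided 95% interval is 0 to 11.6% (0 to 7.1%). If 30 (50) subjects are in the effectiveness analysis set and all succeed, it is 88.4 to 100% (92.9 to 100%).*

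The cost is one extra table column and a sample size statement that reads less favourably. No subjects are added, and no procedure or design element changes.

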### 14.4. Analyses to be conducted

### 14.4.1. General Conventions

Standard descriptive summaries for continuous data include the number of observations with data, mean, standard deviation (SD), median, minimum, and maximum values. The mean and median will be rounded to one decimal place greater than in the raw data where applicable; the standard deviation will be rounded to two decimal places greater than in the raw data where applicable. In cases where this is not applicable (e.g., average time spent), the mean will be rounded to one decimal place; the standard deviation to two decimal places; the minimum and maximum to the nearest whole number. These will be referred to as "continuous summaries" in this document.

For categorical data, the count and percent will be provided. Percentages will be based on the number of subjects without missing data. For adverse event and device effects data, percentages will be based on the number of subjects in the analysis population being used in the analysis. When count data are presented, the percentage for zero counts will be suppressed in order to draw attention to the non-zero counts. Frequency counts will be presented as whole numbers and

percentages will be rounded to one decimal place. This will be referred to as "categorical summaries" in this document.

Adverse events (AE) tables will be sorted by decreasing frequency of events, unless otherwise specified.

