# 3.2. Study Endpoints

#### 3.2.1. **Primary Endpoint(s)**

The primary endpoint is to confirm pulmonary vein isolation. This is defined as confirmation of entrance block in all targeted PVs after adenosine and/or isoproterenol challenge using the nGEN/ QDOT Micro Ablation System.

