### • During the AF Ablation procedure

- Administer a heparin bolus PRIOR to transseptal puncture.
- Target an ACT of at least ≥325 seconds, prior to or immediately following transseptal puncture and throughout the procedure.
- It's strongly recommended to check ACT levels on regular basis during the procedure to ensure an ACT target of at least ≥325 seconds
- Adenosine or isoprotenerol challenge is mandatory for the purposes of this study unless the subject is contraindicated for one of these medications.
  - Adenosine: A (12 to 24 mg) to confirm PV isolation; rule out dormant conduction OR
  - O Isoproterenol to achieve a ≥20 beats per minute increase in heart rate to induce AF upon completion of the ablation procedure is recommended if pacing maneuvers are not performed (recommended dose range is 2-20 mcg/min).
- Following the AF Ablation procedure
  - Anticoagulation therapy is strongly recommended for at least 2 months following ablation.
  - Additional medications needed to treat clinical indications are at the discretion of the clinical investigation physician.
  - AAD management during the study will be at the discretion of the investigator

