## 14.2. Analysis Sets

The following analysis populations will be used to complete the analyses of data:

- **Safety Analysis Set**: The Safety Analysis Set will include all enrolled subjects who have the investigational device inserted, regardless if RF energy is delivered.
- Effectiveness Analysis Set : The effectiveness analysis set will include all enrolled subjects who meet the study eligibility criteria, have the investigational device inserted and undergo an ablation procedure with the study catheter used in conjunction with QMODE+ and /or QMODE for PVI (RF energy is delivered). The subjects without any QMODE+ applications for PVI will be considered a failure.

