### 14.4.7. Handling of Missing Data

Missing data will not be imputed. All analyses will be performed using observed data.

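### The plan does not say how to score confirmed entrance block without a drug challenge, and its missing-data convention could drop treated subjects from the primary denominator

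*Combined protocol and SAP*

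**What the plan says.** **Endpoint.** Section 3.2.1 defines success as "confirmation of entrance block in all targeted PVs after adenosine and/or isoproterenol challenge", using the study ablation system. Either drug satisfies this wording. The procedure description in the Protocol Summary lists the step as "Confirmation of entrance block with adenosine/isoproterenol challenge" and mentions no waiver.

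**Waivers.** Section 7, on medication during the procedure, says the "challenge is mandatory for the purposes of this study unless the subject is contraindicated for one of these medications". Section 8.2.2.3 offers either drug but ties its exemption to contraindication to adenosine only. The sequence in 8.2.2.3 then ends with confirming entrance block in the targeted veins, as a separate step with no exemption attached.

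**Analysis set and scoring.** Under Section 14.2 the effectiveness set needs eligibility, device insertion and RF delivery for PVI. It does not need a challenge or a completed final assessment. Section 14.2 gives one scoring rule: "The subjects without any QMODE+ applications for PVI will be considered a failure".

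**Analysis.** Section 14.4.4 states: "Acute procedural success will be summarized using categorical summaries for the effectiveness analysis set". It adds a listing.

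**Denominator.** Section 14.4.1 sets the percentage base for categorical data: "Percentages will be based on the number of subjects without missing data". The next sentence makes an exception: "For adverse event and device effects data, percentages will be based on the number of subjects in the analysis population" being used. Section 14.4.7 adds: "Missing data will not be imputed. All analyses will be performed using observed data".

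**The concern.** Two gaps meet at the same endpoint.

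First, the endpoint definition includes a step that the procedure rules sometimes excuse. A subject can follow the protocol, have block confirmed in every targeted vein, receive neither drug, and still not meet Section 3.2.1 as worded. The plan does not say whether that subject is a success, a failure or missing.

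Second, the general percentage convention applies to the primary endpoint because Section 14.4.4 uses categorical summaries and states no exception. Three kinds of treated subject could be recorded as missing: one whose procedure stopped after RF delivery, one whose final assessment was not done, and one whose challenge was omitted. All three are in the effectiveness set, and each would leave the denominator if coded missing. For the stopped subject that conflicts with the endpoint definition, under which unconfirmed block is not success.

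At stake is the headline rate of a study with 30 to 50 subjects and one primary endpoint. If the scoring is settled after outcomes are known, it could decide whether the report shows 100%.

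**Working it through.** The plan states no success rate, power or threshold, so there is no figure to reproduce. The check has two parts: whether the text leads where the concern says, and what one affected subject is worth.

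**Reading the text**

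1. Section 14.4.4 sends the primary endpoint to categorical summaries.
2. Section 14.4.1 bases those percentages on non-missing data and reserves the analysis-population base for adverse event and device-effect data.
3. Section 14.4.7 bars imputation.
4. Section 14.2 keeps in the set any eligible subject who had RF delivered for PVI. Section 4.5 reserves the discontinued category for subjects with no RF delivered, so a procedure stopped after RF stays in the effectiveness set.
5. The scoring rule in Section 14.2 concerns absence of QMODE+ applications only. It covers neither an omitted challenge nor an unfinished assessment.

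Naming the effectiveness set in 14.4.4 says who is eligible for the analysis. The percentage base within that set still comes from 14.4.1, and it shrinks only when an outcome is recorded as missing.

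**Size per subject**

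Inputs: n = 30 and n = 50, the ends of the range in Section 14.3, taken as the size of the effectiveness set. The numbers of affected subjects and of other failures are assumptions, because the documents give neither.

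*Case A: one stopped subject, all others successful.* With s = n − 1 successes, dropping gives s/(n − 1) and counting gives s/n. The difference is 1/n.

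- n = 30: 29/29 = 100% against 29/30 = 96.7%, a difference of 3.3 points.
- n = 50: 49/49 = 100% against 49/50 = 98.0%, a difference of 2.0 points.

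*Case B: one subject with challenge omitted or final assessment not done, plus one other failure.* With s = n − 2 clear successes, the candidate rates are s/n (not met), s/(n − 1) (dropped) and (s + 1)/n (success).

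| n | Not met | Dropped | Success |
|---|---|---|---|
| 30 | 28/30 = 93.3% | 28/29 = 96.6% | 29/30 = 96.7% |
| 50 | 48/50 = 96.0% | 48/49 = 98.0% | 49/50 = 98.0% |

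From unrounded values, dropping minus not met is 96.55 − 93.33 = +3.2 points at n = 30 and 97.96 − 96.00 = +2.0 at n = 50. Dropping minus success is 96.55 − 96.67 = −0.1 and 97.96 − 98.00 = −0.04.

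In case A dropping always raises the rate. In case B the direction depends on the subject's true status, which is unknown. If dropping lowers the rate, it does so by very little.

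**The case against.** The strongest reply is that the problem is mostly hypothetical. The endpoint is determined in the laboratory on the day of the procedure. Section 8.2.2.3 expects ablation to continue until isolation is confirmed and ends with a confirmation step that carries no waiver. Missing data are tracked and queried (Sections 17 and 18.1.3). A non-missing percentage base is an ordinary general convention. The failure rule in Section 14.2 also suggests that members of the set are meant to be scored, not dropped. The eCRFs, which are not in the documents, may settle the coding.

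Much of this stands, and it limits both likelihood and size. It does not supply the missing rule. The 8.2.2.3 sequence is headed as recommended, and it lets the investigator interrupt RF delivery at any time. Section 14 presents itself as the statistical analysis plan, and nothing in it settles the coding.

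A reader might infer three stronger things, and the documents support none of them:

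- **That the primary rate is not based on the effectiveness set.** Section 14.4.4 names that set, and nothing says that a subject with a stopped procedure or an omitted challenge is coded missing.
- **That every subject contraindicated for one drug falls outside the endpoint.** Section 3.2.1 accepts either drug, so the gap concerns only a subject who receives neither.
- **That the reported rate is biased upward.** For omitted challenges and unassessed outcomes the direction is unknown, and the number affected may be zero.

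The absence of a waiver in the Protocol Summary is normal abbreviation and adds little.

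**Conclusion.** The point holds and is minor. Section 3.2.1 requires a challenge that Sections 7 and 8.2.2.3 excuse in differing words, and no rule scores a subject with confirmed block and no challenge. Separately, Sections 14.4.1 and 14.4.7 allow a treated subject without confirmed block to leave the primary denominator if the outcome is recorded as missing, against the endpoint's own definition.

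Each affected subject is worth at most about 3.3 points at n = 30 and 2.0 points at n = 50 in the one-subject cases worked above. These are illustrations resting on assumed counts, not a forecast. No hypothesis, threshold or error rate is touched (Sections 14.1 and 14.3), and the counts, the disposition summary and the primary-endpoint listing would let a reader trace a dropped subject. Tracing a choice afterwards is not the same as fixing it beforehand, so the wording is still worth correcting.

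**What to change.** In Section 14.4.4:

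1. State that the denominator for the primary endpoint is the full effectiveness analysis set, as an exception to 14.4.1 and 14.4.7. Section 14.4.1 already uses the analysis population in this way for adverse events.
2. State that any subject without confirmed entrance block in every targeted vein counts as not successful.
3. Prespecify one scoring for block confirmed with the challenge omitted. If the wording of 3.2.1 stands, that scoring is not met. Another choice would also close the gap, provided it is fixed in advance and 3.2.1 is worded to match.
4. Report in one line how many such subjects there were and the rate under the alternative scoring.

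Reconcile the waiver wording in Sections 7 and 8.2.2.3 with each other and with 3.2.1. Which condition is clinically right is not judged here.

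The cost is a few sentences in the SAP and a line in the primary table. The reported rate may come out slightly less favourable.
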